5.6.5 Other Safety Endpoints

Other safety endpoints include hematology and biochemistry laboratory values, vital signs, physical examination and ECG findings.

Physical examination and ECG findings will be summarized as categorical variables (Normal, Abnormal not clinically significant, Abnormal clinically significant) by visit.

Hematology and biochemistry laboratory values and vital signs (heart rate, systolic blood

pressure, diastolic blood pressure, temperature, height and weight) will be summarized as continuous variables by visit.

The percentage of subjects who missed 1 or more dialysis visits during the Double-blind Treatment Period will also be summarized.

Each of the above parameters will be listed by subject and, if applicable, visit.

6 Appendices

6.1 Handling of Missing or Incomplete Dates for Adverse Events , Prior and Concomitant Medications

Adverse Events

Handling of partial dates is only considered for the start date. An adverse event with a partial start date is considered treatment emergent if:

- only the day is missing and the start month/year is the same or after the month/year of the first application
- the day and month are missing and the start year is the same or greater than the year of the first application date
- the start date is completely missing

Prior and Concomitant Therapies

A medication or therapy is considered prior medication or therapy if:

- only the day is missing and the start month/year is prior to the month/year of the treatment start date.
- the day and month are missing and the start year is the same or before than the year of the first dose date
- the start date is completely missing or the medication is not-ongoing.

A medication or therapy is considered concomitant medication if:

- only the day is missing and the stop month/year is the same or after the month/year of the first dose
- the day and month are missing and the stop year is the same or greater than the year of the first dose date
- the stop date is completely missing or the medication is ongoing.

A medication is considered both prior and concomitant if the start date is before the treatment start date and the stop date is after treatment start date or if the medication is ongoing.

Section	Detail
3.3	Percentage of subjects obtaining a complete response in weekly WI-NRS recorded in the subjects' diaries from Baseline to Week 1, Week 4, Week 8 and Week 12.
	As per protocol version 2.0 dated 24 Aug 2022, complete response is defined as scored equal to 0 or 1 in >80% of the non-missing WI-NRS values recorded in subjects diaries 7 days prior to and including the scheduled in clinic visits. Additional tables using the threshold value of 70% will be developed. This is justified by published paper as given below:
	CR845-310302: A Study to Evaluate the Safety and Efficacy of Difelikefalin in Advanced Chronic Kidney Disease Patients With Moderate-to-Severe Pruritus and Not on Dialysis
	Efficacy Assessment Phase (Treatment Period 1): Proportion of subjects who are "complete itch responders" defined as subjects with \geq 70% of the non-missing 24-hour WI-NRS scores equal to 0 or 1 at Week 12 of Treatment Period 1. [Time Frame: Week 12 of Treatment Period 1]
	Intensity of itch will be measured using an NRS used to indicate the intensity of the worst itching over the past 24 hours using a 0 to 10 numeric rating scale, where "0" represents "no itching" and "10" represents "worst itching imaginable".
	https://clinicaltrials.gov/ct2/show/NCT05356403?term=cr845&draw=3&rank=20
3.6	Deleted analysis as described in Section 4.2 Protocol, Other endpoints -Changes in biomarkers in skin punch biopsy samples from Baseline to Week 12 for MC2-25 cream compared to MC2-25 vehicle.

6.2 Changes in analyses from protocol:

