7.12.2 Reporting of adverse events

Adverse event information will be collected from individual trial subjects from signature of the informed consent form until the last trial visit.

If the event is reported as an SAE, the timelines for SAE reporting apply (see Section 7.12.10). If the event is reported as non-serious AE, it should be reported on the appropriate eCRF page.

All SAEs and related non-serious AEs must be followed by the investigator until they are resolved or until judged by the investigator to be stable/needing no further follow-up. All

relevant follow-up information will be reported in the eCRF (and to PharmaLex if it qualifies as an SAE, see Section 7.12.1).

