5.6.4 Adverse Events

Adverse events (AE) will be coded using MedDRA version 24.1 terminology. Treatmentemergent adverse events (TEAEs) related TEAEs (unlikely related, possibly related, and probably related), non-serious TEAEs, serious TEAEs (TESAEs), related TESAEs, TEAEs leading to treatment discontinuation or trial withdrawal, and deaths will be summarized for the overall incidence of at least one event, incidence by SOC and incidence by SOC and PT.

By definition, TEAE is an AE that began after the start of trial medication treatment. TESAE's are any TEAE's that are reported as serious in the eCRF.

Each subject will contribute only once to each of the incidence rates, regardless of the number of occurrences (events) the subject experiences. The number of occurrences for each SOC and PT will also be displayed.

TEAEs will also be descriptively summarized by severity (mild, moderate or severe) and by relationship to IMP [not related or related (unlikely related, possibly related and probably related)]. In summaries of severity and relationship, subjects who report more than one event mapped to the same SOC or PT will be counted only once under the strongest severity and relationship, accordingly.

An AE is treatment-emergent if its date of onset in on or after the first application date of IMP. An AE is related if relationship to IMP is assessed as unlikely related, probably related, or possibly related.

TEAEs, TESAEs, TEAEs leading to treatment discontinuation or study withdrawal and deaths will be listed by subject.

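### SAP 6.1 decides treatment emergence from the start date alone, so an adverse event with a recorded stop before first application still counts as a TEAE when its start date is incomplete

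*SAP*

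**What the plan says.** SAP 6.1 sets the rule for adverse events with incomplete dates. It opens with "Handling of partial dates is only considered for the start date" and then makes an event treatment-emergent in any of three situations:

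- The first concerns an unknown day: "only the day is missing and the start month/year is the same or after the month/year of the first application".
- The second concerns a start known only by its year. Such an event counts when that year equals or follows the year of first application.
- The third covers an event with no start information at all: "the start date is completely missing".

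The general definition is in SAP 5.6.4: "An AE is treatment-emergent if its date of onset in on or after the first application date of IMP". Protocol 8.7.1 defines it in the same way.

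Protocol 7.12.2 collects adverse events "from signature of the informed consent form until the last trial visit". Protocol Table 3 places screening at Day -28 to Day -1, and Protocol 7.12.1 has both start and stop dates recorded in the eCRF.

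For medications, SAP 6.1 compares the stop date with first dose when deciding whether a therapy is concomitant. Its third condition for a prior therapy reads "the start date is completely missing or the medication is not-ongoing". SAP 5.6.3 defines a prior therapy by a start date before the first IMP application.

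**The concern.** Consent can precede first application by up to four weeks, so the database can hold adverse events that began and resolved before any cream was used. With a complete start date, such an event is correctly excluded from the TEAE tables. If part of the start date is missing, SAP 6.1 can bring it in, even though the recorded stop date shows that it was over before treatment.

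TEAE frequency is the first safety endpoint listed in SAP 3.5, and Protocol 2.3 describes this as the first clinical trial of the cream. The table should not include events that the data show to have preceded exposure. The percentages are also sensitive to single subjects, because the planned vehicle arm has only 36.

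The prior-therapy rule has a similar defect. Read as written, a medication with an incomplete date that is known to have started and stopped during treatment is classed as prior, because it is no longer ongoing.

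**Working it through.** The documents give no figure for this rule, so there is none to reproduce. The check has three parts.

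**1. Apply the rule to one event.** Take first application on 20 March 2023 and an event that ran from 8 to 12 March 2023 (invented dates).

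| Start date on file | SAP 6.1, or 5.6.4 if complete | With a stop-date check added |
|---|---|---|
| 8 March 2023 | not a TEAE | not a TEAE |
| March 2023, day missing | TEAE | not a TEAE |
| 2023, day and month missing | TEAE | not a TEAE |
| Missing | TEAE | not a TEAE |
| February 2023, day missing | not a TEAE | not a TEAE |
| 2022, day and month missing | not a TEAE | not a TEAE |

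The last two rows show different start information for comparison: a start known only to an earlier month or year is handled correctly. The error is confined to rows two to four. An event that ended on 12 March cannot have begun on or after 20 March, so in those rows SAP 6.1 gives the opposite answer to SAP 5.6.4 and Protocol 8.7.1.

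**2. Share of pre-dose events misfiled, given an incomplete start date.** Assumptions: the full 28-day screening period is used, onset is uniform over the 28 days before Day 0, and Day 0 is uniform over a 365-day year. That gives 365 × 28 = 10,220 pairs of Day 0 and onset day.

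- *Only the day missing.* The event is misfiled if onset and Day 0 share a calendar month. For Day 0 on day j of the month, min(j − 1, 28) of the 28 onset days qualify. Summed over j, this is 462 for a 31-day month, 434 for a 30-day month and 378 for February. Total: 7 × 462 + 4 × 434 + 378 = 5,348, and 5,348 / 10,220 = 52.3%.
- *Day and month missing.* The event is misfiled if the calendar year is shared. The pairs that cross New Year number 28 + 27 + … + 1 = 406, so (10,220 − 406) / 10,220 = 96.0%.
- *Start date missing.* 100%.

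The 52.3% is somewhat high. The events at issue must also have ended before Day 0, and those starting just before Day 0, which are most likely to share its month, are least likely to have ended. Weighting each onset k days before Day 0 by 1 − exp(−k/m), where m is an assumed mean duration, gives for the day-missing case:

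| Screening length | No weighting | m = 3 days | m = 7 days | m = 14 days |
|---|---|---|---|---|
| 28 days | 52% | 49% | 45% | 42% |
| 21 days | 64% | 60% | 58% | 56% |
| 14 days | 75% | 72% | 71% | 69% |

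With day and month missing, the 28-day figure stays at 95% to 96%.

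**3. Effect of one event on a TEAE percentage.** With the planned 72 and 36 subjects, one extra subject is 1/72 = 1.4 percentage points for cream or 1/36 = 2.8 for vehicle. This applies only if the subject has no other TEAE in that row, because SAP 5.6.4 counts each subject once per rate. Under 2:1 allocation such an event falls in the cream arm about twice as often.

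**Medication rule.** The heading of SAP 6.1 limits it to missing or incomplete dates; fully dated therapies follow SAP 5.6.3. Take a drug with a start month after the month of first application, the day unknown, and a recorded stop. It fails the first prior-therapy condition but meets the not-ongoing clause of the third. It therefore appears in the prior-therapy summary although it is known to have started on treatment.

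**The case against.** The strongest reply is that the opening sentence may mean only that partial stop dates get no rule of their own. On that reading a complete stop date is not expressly disregarded, the onset definition still governs, and SAP 6.1 is a cautious default for unknown onset. The caution is reasonable and should be kept. But the reading does not rescue the text. The three conditions say outright that such an event is considered treatment-emergent, and neither document adds a stop-date exception. Where the stop date is known to precede treatment, there is no doubt left to be cautious about.

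Several points about size do stand. Pre-dose events precede treatment in a randomised, double-blind trial, and SAP 5.6 makes safety analysis descriptive. Protocol 7.4 to 7.6 and 7.8 send clinically significant abnormalities seen at the Screening visit to medical history, which reduces the number of pre-dose events. The visit schedule marks adverse events only from Baseline, although Protocol 7.12.2 is explicit that collection starts at consent. The subject listings should let a reader spot an early stop date.

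A reader might infer three stronger things that the documents do not support:

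- *That the rule biases the safety comparison.* Nothing suggests that incomplete start dates for pre-dose events would differ by arm.
- *That it would materially fill the related and serious TEAE tables.* SAP 5.6.4 does count unlikely-related events as related. However, Protocol 7.12.4 lets the investigator call an event not related when timing makes causality clearly improbable, and 24-hour serious-event reporting makes a missing start date unlikely.
- *That every stopped medication is classed as prior.* Given the scope of SAP 6.1 and the definition in SAP 5.6.3, this is limited to therapies with incomplete dates.

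**Conclusion.** The point holds as a minor classification error. For an adverse event whose stop date precedes first application, SAP 6.1 returns a TEAE whenever the start date is missing or is known only to the same month or year as first application, contrary to SAP 5.6.4 and Protocol 8.7.1.

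The shares in the working are conditional on a pre-dose event having an incomplete start date. They also rest on the assumptions of uniform onset, screening length and event duration. The documents do not say how often start dates will be incomplete, so the expected number of misfiled events cannot be calculated; it is probably small. The consequence is noise in descriptive tables, not a shift towards either arm. The medication defect is real within the same limits.

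**What to change.** Add one clause to the adverse-event part of SAP 6.1: *An AE whose stop date (complete, or partial but unambiguously earlier) is before the first application is not treatment-emergent, whatever is missing from its start date.* Leave the three existing conditions as the default for all other incomplete start dates.

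In the prior-therapy part of SAP 6.1, delete the not-ongoing alternative from the third condition, so that an incompletely dated drug known to have started on treatment is not classed as prior. This agrees with SAP 5.6.3.

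The cost is two short SAP edits and the matching conditions in the derivation programs. Stop dates are already collected, so no new data are needed. The edits should be made before unblinding, because reclassifying TEAEs afterwards could look driven by the results.

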6.3 Reference Materials

6.3.1 EQ-5D-5L Index Value

The EQ-5D-5L descriptive system comprises five dimensions (5D). The respondent is asked to indicate his/her health state by checking the box next to the most appropriate response level for each of the five dimensions.

A unique health state is defined for each subject by combining one level from each of the five dimensions. A total of 3125 possible unique health states is defined in this way. Each state is referred to by a 5-digit code.

For example, working clockwise from the top of the diagram, state 12345 indicates no problems with mobility, slight problems with washing or dressing, moderate problems with doing usual activities, severe pain or discomfort and extreme anxiety or depression, while state 11111 indicates no problems on any of the five dimensions and 55555 indicates extreme problems at each dimension.

EQ-5D-5LUserGuide Basic information on how to use the EQ-5D-5L instrument Version3.0

https://euroqol.org/eq-5d-instruments/eq-5d-51-about/valuation-standard-value-sets/

Parallel Valuation of the EQ-5D-3L and EQ-5D-5L by Time Trade-Off in Hungary

DOI link: https://doi.org/10.1016/j.jval.2020.03.019

Published Print: 2020-09

Valuation of EQ-5D-5L Health States in Poland: the First EQ-VT-Based Study in Central and Eastern Europe

Crossref DOI link: https://doi.org/10.1007/s40273-019-00811-7

Published Print: 2019-09

Value Sets for EQ-5D-5L- A Compendium, Comparative Review & User Guide

https://doi.org/10.1007/978-3-030-89289-0

Valuing health-related quality of life: An EQ-5D-5L value set for England

DOI: 10.1002/hec.3564

German Value Set for the EQ-5D-5L

https://doi.org/10.1007/s40273-018-0615-8

6.3.2 Systemic treatment CKD-aP can be identified via ATC code Level 3 or 4:

R06A Antihistamines for systemic use
R06AA Aminoalkyl ethers
R06AB Substituted alkylamines
R06AC Substituted ethylene diamines
R06AD Phenothiazine derivatives
R06AE Piperazine derivatives
R06AK Combinations of antihistamines
R06AX Other antihistamines for systemic use
H02A Corticosteroids for systemic use, plain
H02B Corticosteroids for systemic use, combinations
For some of them only Level 4 could be the most specific:
N02BF Gabapentinoids
N02BG Other analgesics and antipyretics
